3.3 Primary Study Endpoints

Primary endpoint is a composite of nausea, vomiting, abdominal pain, emergency intubation and aspiration

3.4 Secondary Study Endpoints

- Patient satisfaction
- Incidence of hypoglycaemia (blood sugar < 3.6 mmol/l) as assessed by finger prick test
- Incidence of hypotension (SBP<90 mmHg and /or DBP<60 mmHg)
- 30 day chest infection rate

3.5 End of study

Data collection will start November 2017 and we will continue until the 400 patients are enrolled or premature termination of the study due to safety issue. The last phone contact/ clinic visit will be done 30 days after the enrolment of the last patient.

4 Methods

4.1 Subject Selection and Withdrawal

Once enrolled in the study all patients will be identified by their study number alone and the arm of the study they are involved in. If the patient decides to withdraw from the study at any point after randomization, they will revert to the standard hospital procedure policy of fasting. However, they will still be included in the final analysis as intention to treat and any drop out or cross over will be documented.

4.1.1 Inclusion Criteria

- All patients >18 years undergoing elective coronary angiography or angioplasty procedures in the 2 months window.

4.1.2 Exclusion Criteria

- Patient choice
- Other cardiac procedures such as EP studies, pacing, structural heart disease intervention
- Emergency PPCI
- Patients already admitted in the hospital with UA / NSTEMI
- Patients unable to give informed consent (vulnerable group)

4.2 Subject Recruitment and Screening

All patients undergoing elective cardiac catheterisation procedures will be sent an invitation in the post including the patient information leaflet together with their pre-procedure assessment date. This will allow them to read about the study prior to the assessment to decide whether they would like to be included. Once at the pre-procedure assessment clinic, the study will be further discussed, any questions will be addressed and the consent form will be signed should they wish to be included.

4.3 Randomisation Process

Randomisation will take place in pre-procedure assessment clinic in a 1:1 ratio using sealed enveloped method. This information (whether fasting or not) will be relayed to the patient at the time of pre-procedure assessment and also stored on a spreadsheet with study number the only identifying factor. This will be password protected with individuals directly involved having access to this. This data will also be backed up on a password protected computer in the catheter laboratory.

4.4 Informed Consent

The patient will receive a detailed description of the study in the patient information sheet sent together with pre-procedure assessment letter by mail (around 1 week before the pre-procedure assessment clinic date). In the pre-procedure assessment clinic, the study will be explained further including potential risks and intended outcome, any patient's question will be addressed, with each

patient given the opportunity to abstain and follow standard procedure. If the patient agrees then they will sign the consent form and then be randomised in a 1:1 ratio to either the fasting or non-fasting group. This will be attached to the inside cover of the notes and checked on the time of presentation on the day of intended procedure.

4.5 Withdrawal of Subjects

If any patient chooses to withdraw from the study, they will revert to the standard hospital procedure. However, they will still be included in the final analysis as intention to treat and any drop out or cross over will be documented.

5 Prior and Concomitant Therapy

All previous medication and treatments should continue.

6 Clinical Procedure

As standard practice, operators will be allowed to use any techniques they commonly use throughout their practice (choice of access, balloon and stent type).

7 Statistical Plan

Given that the occurrence of pulmonary aspiration was so low in similar studies performed for cerebral angiography, we decided against using this as a single primary endpoint as thousands of patients would be required. We opted for a composite primary end point of nausea, vomiting, abdominal pain, emergency intubation and aspiration. These will be recorded both immediately intra/post procedure by the operation physician and again by the patient within 8 hours after the procedure. We will compare the two groups using 95% confidence intervals to ascertain the extent to which they overlap. Secondary end points will be overall patient satisfaction, the incidence of hypoglycaemia and hypotension, and 30 day chest infection rate which will be compared between the two groups.

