Fasting Versus Non-fasting prior to elective Cardiac catheterisation

Chief Investigator: [name]

Principal Investigator: [name]

Research Trust: Blackpool Teaching Hospitals NHS Foundation Trust

Funder: Blackpool Teaching Hospitals NHS Foundation Trust

Sponsor: Blackpool Teaching Hospitals NHS Foundation Trust

Date of Submission: 12/10/2017

Table of Contents

1	STUDY SUMMARY	4
2	INTRODUCTION	6
2.1	BACKGROUND.....	6
2.2	STUDY OBJECTIVES.....	8
3	STUDY DESIGN	9
3.1	GENERAL	9
3.2	STUDY PROCEDURE.....	9
3.3	PRIMARY STUDY ENDPOINTS	10
3.4	SECONDARY STUDY ENDPOINTS	10
3.5	END OF STUDY	10
4	METHODS	10
4.1	SUBJECT SELECTION AND WITHDRAWAL.....	10
4.1.1	Inclusion Criteria	11
4.1.2	Exclusion Criteria	11
4.2	SUBJECT RECRUITMENT AND SCREENING	11
4.3	RANDOMISATION PROCESS	11
4.4	INFORMED CONSENT.....	12
4.5	WITHDRAWAL OF SUBJECTS	12
5	PRIOR AND CONCOMITANT THERAPY	12
6	CLINICAL PROCEDURES	12
7	STATISTICAL PLAN	12
7.1	SAMPLE SIZE DETERMINATION	13
7.2	STATISTICAL METHODS	13
7.3	INTERIM ANALYSES	13
7.4	SUBJECT POPULATION(S) FOR ANALYSIS	13
8	SAFETY AND ADVERSE EVENTS	13
8.1	RECORDING OF ADVERSE EVENTS	14
8.2	EXPECTED NON-SERIOUS ADVERSE EVENTS	14
8.3	SERIOUS ADVERSE EVENTS (SAEs).....	14

8.4	EXPECTED SERIOUS ADVERSE EVENTS	15
8.5	UNEXPECTED AND FATAL SERIOUS ADVERSE EVENTS.....	15
8.6	PERIOD FOR RECORDING SERIOUS ADVERSE EVENTS.....	15
9	DATA HANDLING AND RECORD KEEPING	16
9.1	CONFIDENTIALITY	16
9.2	CASE REPORT FORMS.....	16
9.3	RECORDS RETENTION.....	16
10	STUDY MONITORING, AUDITING, AND INSPECTING	17
11	ETHICAL CONSIDERATIONS.....	17
11.1	PATIENT INFORMATION SHEETS	18
12	FUNDING.....	18
13	SPONSORSHIP	18
14	PUBLICATION PLAN.....	18
15	REFERENCES.....	19

1 Study Summary

Title	Fasting Versus Non-fasting prior to elective Cardiac catheterization
Short Title	Fasting or no fasting before cardiac catheterization
Version & Date	Version 1.7 12 October 2017
Principal Investigator	[name]
Objectives	To show that there is no increased risk of peri-procedural complications between fasting and non-fasting patients as well as improved patient satisfaction when allowed to eat up to the point of elective coronary angiography/angioplasty compared to patients kept nil by mouth. We aim to
Methodology / Design	Prospective single centre, single blinded (investigator) randomized Study Consented patients will be randomised in 1:1 ratio to either standard hospital fasting policy or allowed to eat freely up to the point of transfer to the Catheter Laboratory.

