Duration	12 months
Participating Centres	Blackpool Victoria Hospital
Primary End Point	Composite of nausea, vomiting, abdominal pain, emergency endotracheal intubation and aspiration,
Number of participants	400 patients
Main Inclusion /Exclusion Criteria	INCLUSION

	
1. All patients >18 years undergoing elective coronary angiography or angioplasty procedures in the 2 months window.
 
EXCLUSION
 
 1. Patient choice 2. Other cardiac procedures such as EP studies, pacing, structural heart disease intervention 3. Emergency PPCI 4. Patients already admitted in the hospital with UA / NSTEMI 5. Patients unable to give informed consent

Statistical Methodology and Analysis
	
Our composite primary endpoint will be analysed using 95% confidence interval between the fasting and non-fasting group using the Fisher's exact test. Categorical secondary outcomes will be presented as number and percentages and compared between the two groups using the Chi-square test or Fisher's exact test. Secondary continuous outcomes will be presented as mean and standard deviation and compared using the independent samples t-test. P-values will be used to assess evidence of difference. P value <0.05 will be considered significant.

2 Introduction

This document is a research protocol and this study will be conducted in compliance with the protocol, The Research Governance Framework, International Conference on Harmonisation, Good Clinical Practice Guideline ICH/GCP, and all applicable Blackpool Teaching Hospitals NHS Foundation Trust Research Office requirements.

This study aims to demonstrate that pre procedural fasting for elective cardiac procedures is unnecessary and outdated practice. It is without doubt that induction of general anaesthesia depresses cough and swallow reflexes and therefore increases the risk of aspiration with airway manipulation. However, coronary angiography and angioplasty does not require general anaesthesia and is carried out purely under local anaesthetic. So why do we still need periods of fasting?

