2.2 Study Objectives

- To show that allowing patients to eat freely up to the point of elective coronary angiography/angioplasty is not associated with any increased risk of nausea, vomiting, abdominal pain, emergency intubation or aspiration pneumonia compared to patients kept nil by mouth.
- To show improved patient satisfaction when allowed to eat up to the point of elective coronary angiography/angioplasty compared to patients kept nil by mouth.

We aim to provide evidence from a prospective study to help the development of guidelines that can be implemented nationally and internationally regarding pre procedural care of cardiac patients.

3 Study Design

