7.1 Sample Size Determination

With 200 participants in each group, if none of the participants has an event then the upper limit of the 95% confidence interval for event rate would be 1.5%. Hence if both groups, fasting and non-fasting, have no events recorded then it is highly unlikely that the event rate in the two groups would differ by more than 1.5%. Provided that a difference of 1.5% in event rate is deemed not clinically meaningfully different; then 200 participants in each group would demonstrate that not fasting has a similar event rate to fasting.

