7.2 Statistical Methods

Our composite primary endpoint will be analysed using 95% confidence interval between the fasting and non-fasting group and the event rate will be compared using the Fisher's exact test. Categorical secondary outcomes will be presented as number and percentages and compared between the two groups using the Chi-square test or Fisher's exact test. Secondary continuous outcomes will be presented as mean and standard deviation and compared using the independent samples t-test. P-values will be used to assess evidence of difference. Any P value < 0.05 will be considered significant.

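### The trial aims to show no increased risk from eating, but no rule compares a confidence interval for the risk difference with a margin; CI overlap and a Fisher test of difference cannot support that aim

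*Combined protocol and SAP*

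**What the plan says.** **Aim.** The first objective in the Study Summary is "To show that there is no increased risk of peri-procedural complications between fasting and non-fasting patients". Section 2.2 aims to show that eating freely "is not associated with any increased risk of nausea, vomiting, abdominal pain, emergency intubation or aspiration pneumonia" compared with nil by mouth. Both are claims of absence of harm.

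**Analysis.** The opening of section 7 says "We will compare the two groups using 95% confidence intervals to ascertain the extent to which they overlap", without saying what extent of overlap means what. The Study Summary plans a "95% confidence interval between the fasting and non-fasting group using the" Fisher's exact test. Section 7.2 has a "95% confidence interval between the fasting and non-fasting group and the event rate will be compared using" Fisher's exact test, treats P-values as evidence of difference, and sets significance at P<0.05. Neither place names the effect measure, the CI method or an acceptance threshold.

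**Sample size.** Section 7.1 argues that with 200 per group, "if none of the participants has an event then the upper limit of the 95% confidence interval for event rate would be 1.5" per cent. It then sets a condition: "Provided that a difference of 1.5% in event rate is deemed not clinically meaningfully different". The conclusion it draws under that condition reads: "then 200 participants in each group would demonstrate that not fasting has a similar event rate to fasting". The argument covers only the case of no events in either group.

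**The concern.** To support a claim of no increased risk, the data must exclude an excess large enough to matter. That needs an upper confidence limit for the difference and a margin to hold it against. A non-significant Fisher test shows only that a difference was not detected. Overlap of two separate intervals is weaker still, because intervals can overlap when the difference is significant.

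For example, 8 events with non-fasting and 2 with fasting (4% v 1%) gives Fisher P=0.105 and overlapping exact CIs. The Newcombe 95% CI for the difference is −0.2 to 6.8 points. Under the plan as written this could be reported as no increased risk, although it is a fourfold observed excess and the interval reaches nearly 7 points. Nothing in the plan would call it inconclusive.

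The two planned criteria can also conflict, and no precedence is stated. What is at stake is a safety conclusion that section 2.2 intends as evidence for national and international guidelines.

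**Working it through.** **Inputs from the documents.** 200 per arm, 1:1; 95% level; P<0.05; the conditional 1.5% (section 7.1); an expected nausea and vomiting rate of 1–2% (section 11).

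**Assumptions.** The 1–2% is used for the whole composite. The non-fasting rates of 2.5%, 4% and 5% are illustrations and do not come from the documents. Arm-wise intervals are exact (Clopper–Pearson). Intervals for the difference (non-fasting minus fasting) are Newcombe.

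**1. Reproduce the 1.5%.** For 0/200 in one arm:
- Rule of three: 3/200 = 1.50%.
- Exact one-sided 95%: 1 − 0.05^(1/200) = 1.49%.
- Exact two-sided 95%: 1 − 0.025^(1/200) = 1.83%.

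So 1.5% is a one-sided limit for a single arm. Section 7.1 states neither the sidedness nor a limit for the difference.

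**2. Upper limit for the difference.** Newcombe: U = d + √[(u₁ − p₁)² + (p₂ − l₂)²], where l and u are Wilson limits for each arm.
- 0 v 0: U = z²/(200 + z²). Two-sided 95%: 3.84/203.84 = 1.88 points. One-sided 95%: 2.71/202.71 = 1.33 points.
- 1 v 1, two-sided 95%: Wilson limits 0.09% and 2.78%, so U = √[(2.78 − 0.50)² + (0.50 − 0.09)²] = 2.31 points. One-sided 95%: 1.75 points.

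The zero-event statement in 7.1 therefore holds at its own one-sided level but not under a two-sided 95% CI. With one event per arm, 1.5 points is exceeded at either level.

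**3. How often the 7.1 case arises.** P(no events in 400) = (1 − p)^400, which is 1.8% at p = 1% and 0.03% at p = 2%.

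**4. What the planned methods would do.** Full enumeration of Binomial(200, p) counts in each arm; the third column is the chance that Fisher's test does not show non-fasting to be significantly worse:

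| True rates, fasting v non-fasting | Fisher does not flag excess | Exact CIs overlap | Upper 95% limit <1.5 points, two-sided / one-sided |
|---|---|---|---|
| 1% v 2.5% | 90% | 99% | 2.1% / 4.0% |
| 1% v 4% | 64% | 89% | 0.2% / 0.4% |
| 2% v 5% | 73% | 93% | 0.2% / 0.6% |
| 1% v 1% | n/a | n/a | 22% / 34% |
| 2% v 2% | n/a | n/a | 15% / 23% |

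**5. Conflict between the two criteria.** At 10 non-fasting v 2 fasting events, Fisher P=0.036, yet the exact CIs (2.42–9.00% and 0.12–3.57%) overlap. With 2 fasting events, Fisher's test is significant from 10 non-fasting events, but the intervals separate only from 14. At 1% v 4%, Fisher is significant while the CIs overlap in 25% of trials.

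**The case against.** **It is a pilot.** Sections 7.3 and 12–14 say so, and section 14 plans a larger study to prove the result. Estimation with CIs is a legitimate pilot aim. This softens the impact, but the sample-size section claims demonstration and section 2.2 aims at guidelines. Either those claims need a rule or they need to be toned down.

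**The elements are partly there.** Section 7.1 names a 1.5% difference and links it to a confidence limit, and the interval in 7.2 can be read as a CI for the difference. Both are fair readings. Even so, no sentence compares that interval with 1.5% or any other value, and the 1.5% is conditional and confined to zero events.

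**Overlap may be meant descriptively.** Section 7 speaks of its extent, so the overlap percentages above impose a yes/no reading that the section does not state. If it is only descriptive, however, the plan has no criterion at all for its aim.

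**The rates are uncertain.** The 1–2% excludes abdominal pain, intubation and aspiration, and the higher non-fasting rates are the reviewer's choice. They show the size of the problem and are not predictions.

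**Being below a margin does not prove zero excess.** This is correct: it shows only that any increase is smaller than the margin. The fix is worded accordingly.

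**Conclusion.** The concern holds and must be fixed. The aim is absence of harm, the planned analyses look for a difference or for overlap, and no result is defined as supporting the aim or as inconclusive. Under the stated assumptions, a rise from 1% to 4% would go unflagged by Fisher's test in 64% of trials and leave overlapping CIs in 89%. A 1.5-point rule on the difference would wrongly support the claim in only 0.2% (two-sided 95%) or 0.4% (one-sided 95%).

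The claim in 7.1 that 200 per group suffices is not supported once events occur. With equal true rates of 1–2%, the 1.5-point rule is met in 15–22% of trials (two-sided 95%) or 23–34% (one-sided 95%). That the documents lack a decision rule depends on none of these rates; only the percentages do.

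**What to change.** - **Study Summary, 7 and 7.2.** Make the primary analysis the risk difference (non-fasting minus fasting) with a CI of stated level and sidedness, by one named method suited to rare events (Newcombe or Miettinen–Nurminen). A two-sided 95% CI matches the 95% CIs and P<0.05 already planned.
- **Decision rule.** If the lower limit exceeds 0, conclude increased risk. Otherwise, conclude no increase beyond the margin only if the upper limit is below it. Anything else is inconclusive.
- **Overlap and Fisher.** Delete the overlap criterion in section 7. Sections 7.3 and 8 also rely on non-overlapping intervals for stopping, and need to be reconciled with the change. Keep Fisher's P as descriptive and state that the CI rule prevails. At 9 v 2, for example, P=0.062 but the CI is 0.2 to 7.4 points, so the conclusion is increased risk.
- **Section 7.1.** Replace the claim of demonstration with the expected precision for the difference. The upper limit at 0 v 0 is 1.9 points (two-sided 95%) or 1.3 (one-sided 95%); at 1 v 1 it is 2.3 or 1.8.
- **Margin.** Fix it on clinical grounds, not from n=200, before the first patient is randomised. If enrolment has begun, people without access to events by arm should set it, because section 8 has the Chief Investigator monitoring the data continuously.
- **Alternative.** If no margin is fixed, report the pilot as estimation, reword the objectives from showing to estimating, and leave the confirmatory test to the larger study.

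**Cost.** The wording and the calculation are cheap; the real cost is in the conclusion. With a 1.5-point margin and equal true rates of 1–2%, the result is inconclusive in 77–83% of trials (two-sided 95%), or 65–75% if the upper limit is one-sided 95%. An 80% chance of meeting 1.5 points needs about 850 (at 1%) to 1450 (at 2%) per arm at two-sided 95%, or 650 to 1150 at one-sided 95%. The CI rule and Fisher's test will sometimes visibly disagree: at 1% v 4%, the lower limit exceeds 0 with P≥0.05 in 10% of trials.

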7.1 Sample Size Determination

With 200 participants in each group, if none of the participants has an event then the upper limit of the 95% confidence interval for event rate would be 1.5%. Hence if both groups, fasting and non-fasting, have no events recorded then it is highly unlikely that the event rate in the two groups would differ by more than 1.5%. Provided that a difference of 1.5% in event rate is deemed not clinically meaningfully different; then 200 participants in each group would demonstrate that not fasting has a similar event rate to fasting.

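### The 1.5% that justifies 200 per group in section 7.1 is a one-sided 95% limit, not labelled as one; in the plan's own 0 v 0 scenario, exact and score-type two-sided 95% limits are about 1.8 to 1.9 points

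*Combined protocol and SAP*

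**What the plan says.** The trial is to enrol 400 patients in a 1:1 ratio (section 3.5: "we will continue until the 400 patients are enrolled"; section 1: "Consented patients will be randomised in 1:1 ratio"). Section 7.1 is the only justification of that number, and it has three steps.

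- For one group of 200, it says that "if none of the participants has an event then the upper limit of the 95% confidence interval for event rate would be 1.5" per cent.
- It carries this to the comparison. Should neither arm show a single event, the section holds that "it is highly unlikely that the event rate in the two groups would differ by more than 1.5" per cent.
- It concludes that 200 per group would demonstrate similarity, on condition that a 1.5% difference is judged clinically unimportant.

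For the analysis, section 7.2 states: "Our composite primary endpoint will be analysed using 95% confidence interval between the fasting and non-fasting group". Event rates are also compared by Fisher's exact test, with significance at P < 0.05. Section 7 adds that the groups' 95% intervals will be examined for overlap. No section says that a limit is one-sided, names a method for the interval on the difference, or sets a decision rule against 1.5%.

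**The concern.** A 95% confidence interval with no further label is read as two-sided, and the rest of the plan (95% intervals, P < 0.05) reads the same way. The figure in 7.1 matches a one-sided limit. If so, the precision promised when the trial was sized is better than the precision that the planned analysis will report, even in the scenario that 7.1 chose for itself.

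This matters because 1.5% does two jobs. It is the only number behind 200 per group, and it is the difference that clinicians are asked to accept as unimportant. If the reported interval reaches 1.9 points, the clinical judgement has been sought at the wrong value.

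**Working it through.** **Inputs.** n = 200 per group (7.1, "With 200 participants in each group"); 0 events in each group (7.1); confidence level 95% (7.1, 7.2); tolerance 1.5 percentage points (7.1); expected nausea and vomiting rate 1–2% (section 11). Sidedness is not stated; two-sided is assumed where noted, with z = 1.96 and z² = 3.8415.

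**1. Reproduce the plan's figure.**
- Rule of three: 3/200 = 1.50%.
- Exact one-sided 95% limit: 1 − 0.05^(1/200) = 1.49%.

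The 1.5% is therefore correct as a one-sided 95% limit for one group.

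**2. The two-sided 95% upper limit for 0/200.**
- Exact (Clopper-Pearson): 1 − 0.025^(1/200) = 1.83%.
- Wilson: z²/(n + z²) = 3.8415/203.8415 = 1.88%.

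**3. The two-sided 95% interval for the difference, 0/200 v 0/200.**
- Newcombe: both observed rates and both lower Wilson limits are 0, so each limit of the difference is the Wilson upper limit: ±1.88 points.
- Miettinen-Nurminen: at 0 v 0 the upper limit d solves d/(1 − d) = z² × (400/399)/200 = 0.01926, so d = 1.89 points.
- Exact unconditional (score ordering): upper limit at least 1.83 points.
- Agresti-Caffo: with p = 1/202, 1.96 × √(2p(1 − p)/202) = ±1.37 points.
- Wald: zero width, so uninformative.

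**4. A check that does not depend on the interval method.** Suppose that the true rates are 0% and 1.5%. Then P(0 v 0) = 0.985^200 = 4.9%. Any method whose interval at 0 v 0 excludes a difference of 1.5 points would miss the truth on that side at least 4.9% of the time. A two-sided 95% interval allows 2.5% per tail. So 0 v 0 can exclude 1.5 points at one-sided 5%, but not at one-sided 2.5%.

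**5. The same scenario at the one-sided 95% (two-sided 90%) level.** The exact single-group limit is 1.49% and the Newcombe interval for the difference is ±1.33 points. Both are within 1.5.

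**6. How likely the zero-event scenario is.** Take the 1–2% of section 11 as the rate in both groups. This is an assumption, and the composite can only be as frequent or more so.
- At 1%: P(0 v 0) = 0.99^400 = 1.8%.
- At 2%: P(0 v 0) = 0.98^400 = 0.03%.
- With one event in each group, the Newcombe 95% interval is already ±2.31 points.

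**The case against.** The strongest reply is that 1.5% is not a miscalculation. It is a familiar and correct one-sided limit, the shortfall is only 0.3 to 0.4 points, 7.1 words the tolerance conditionally, and no decision in section 7 or 7.2 turns on it. All of that stands. It makes this an undeclared level rather than a false sum, and it limits the severity.

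A second reply is that the result depends on a method the plan does not name. Agresti-Caffo is a two-sided 95% interval and gives ±1.37 points; a two-sided mid-P limit for one group is 1.49%; a uniform-prior Bayesian interval for the difference is about ±1.48 points. This also stands as a reason to name the method. It does not rescue the text as written, because none of these guarantees 2.5% error per tail here: at true rates of 0% and 1.5%, 0 v 0 still occurs 4.9% of the time.

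A reader might also infer that moving from one group's limit to the difference is itself an error. It is not, at the one-sided 5% level. If the rates differ by 1.5 points or more, the larger is at least 1.5%, so P(0 v 0) is at most 0.985^200 = 4.9% whatever the smaller rate is.

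Finally, a reader might infer that no result at all could meet the tolerance, or that 0 v 0 is the best case. That holds only if the whole interval must lie within ±1.5. Section 2.2 states the safety objective in one direction, as no increased risk without fasting. On that reading only the upper limit for non-fasting minus fasting counts. With 0 non-fasting and 1 fasting event, the Newcombe 95% interval is −2.78 to +1.43 points; with 0 and 2, the upper limit is +1.02. The documents do not support the stronger claim.

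**Conclusion.** The point holds in limited form. Section 7.1 gives a one-sided 95% limit and calls it the upper limit of the 95% confidence interval. Read as two-sided, the single-group limit is 1.83% (exact) or 1.88% (Wilson), and the 0 v 0 interval for the difference is about ±1.9 points by score-type methods. These are about 22% to 26% above the stated figure (1.83/1.5 = 1.22; 1.89/1.5 = 1.26). The plan's own scenario therefore does not place the two-sided interval within the tolerance that justifies the sample size.

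This rests on two assumptions: that an unlabelled 95% interval is two-sided, and that an exact or score-type method is used, which suits a plan built on Fisher's exact test. It does not show that the trial is too small for its purpose, since a one-sided 95% standard would be met at 0 v 0. The larger practical weakness is the zero-event premise, which section 11's own rate makes improbable; correcting the level does not repair that. Severity: should-fix.

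**What to change.** Keep 400 patients and choose one of two consistent statements.

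- **(a) Two-sided 95%.** In 7.1, say that 0/200 gives an upper two-sided 95% limit of 1.8% per group, and that 0 v 0 gives an interval for the difference of about ±1.9 percentage points. Name the method (Newcombe or Miettinen-Nurminen) in 7.2. Ask for the clinical judgement at 1.9 points instead of 1.5.
- **(b) One-sided 95%.** Keep 1.5%, call it a one-sided 95% (two-sided 90%) limit, and use that level in sections 7 and 7.2.

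Under either option, add to 7.1 that the figure describes precision with no events only. At the 1–2% nausea and vomiting rate of section 11, no events in either group has a probability of at most about 1.8%, and one event per group already widens the interval to ±2.3 points (Newcombe).

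The cost is a few sentences. Option (a) makes the stated precision slightly less favourable; option (b) openly accepts 5% error per tail. Neither needs more patients. For reference, holding a two-sided limit to 1.5% at 0 v 0 would take 245 per group (exact: ln 0.025/ln 0.985 = 244.1) or 253 (Wilson: 3.8415 × 0.985/0.015 = 252.3), which is not proposed here.
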